### 7.8.1 General aspects of response related endpoints

The response assessments during the treatment period follow the scheduled CTs post

baseline, planned for the visits at study weeks 9, 17, 25 (+/- 4 days), and from Week 25 onwards every 8 weeks (+/- 4 days). Unscheduled CT assessments as well as planned CT scans performed on the day of study drug administration [REDACTED]

[REDACTED] are also possible. For patients who are discontinuing all study treatment without having had confirmation of progressive disease (PD) according to iRECIST criteria [Seymour et al], CT assessments are scheduled every 8 weeks (+/- 4 days) after the latest performed CT assessment during the time period they received study treatment.

If not otherwise stated, all response assessments collected by investigator (local assessments) during the study will be considered, regardless of whether they come from scheduled or unscheduled assessments and if they were assessed during or after study treatment.

In principle, any further anti-cancer treatment during the study, i.e. prior to the individual study treatment termination, is prohibited. If nevertheless a patient is treated with further anti-cancer treatment during the study, the inclusion of CT assessments after introduction of further anti-cancer treatment in the derivation of response related and time to event endpoints will be agreed on and documented during the DRM. Also, the non-trial systemic anti-cancer treatments defined in Section 7.8.5 and 7.8.6 will be confirmed during the DRM.

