#### **7.8.6 Progression-free survival (PFS) and overall survival (OS)**

According to RECIST, PFS is defined as the period from the first dose of study drug until PD or death from any cause (whatever occurs first).

PFS is defined as the period from the first dose of study drug until the first time one of following events occurs

- Progression criteria according to iRECIST/RECIST met

- Start of non-trial systemic anti-cancer treatment (which is regarded as progression according to the protocol).
- death from any cause [REDACTED] after last post-baseline CT assessment [REDACTED] after first dose of study drug, if no post-baseline CT assessment is available.

Non-trial systemic anti-cancer treatment is defined as concomitant or post-study treatment/medication that is classified as chemotherapy in the eCRF. Mitotane therapy is not considered as non-trial system anti-cancer treatment.

According to RECIST the progression criteria is met at the first date of post-baseline CT assessment with PD documented as response, if not more than one scheduled CT assessment is missing or not evaluable before this CT assessment and the previous CT assessment was performed within [REDACTED] to this CT assessment.

According to iRECIST the progression criteria is met at the date of CT assessment with response documented as iUPD for that the next CT assessment documents iCPD as response (without any intervening assessments with other outcome), i.e. PD is confirmed, and if not more than one scheduled CT assessment is missing or not evaluable before the CT assessment with iUPD documented and the previous CT assessment was performed within [REDACTED] to CT assessment with IUPD documented. If progression is not confirmed and there is no subsequent CT assessment with iSD, iPR or iCR as response then the iUPD date will still be used as date of progression met in the following scenarios:

- no further response assessments are done or
- the next timepoint responses are all iUPD, and iCPD never occurs.

Non-trial systemic anti-cancer treatment is defined as concomitant or post-study treatment medication that is classified as chemotherapy in the eCRF. Mitotane therapy is not considered as non-trial system anti-cancer treatment.

Patients without an event as defined above will be censored based on the rules in Table 3.

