**Table 3 Censoring rules for PFS**

Situation	Date of Event or Censoring
No CT assessment at baseline	Date of first study treatment administration
No progression nor death nor non-trial systemic anti-cancer treatment documented	Date of last post-baseline CT assessment
Death more than [REDACTED] after last post-baseline CT assessment	Date of last post-baseline CT assessment
Death more than [REDACTED] after first study treatment and without post-baseline CT assessment	Date of first study treatment administration
Progression criteria met after $\geq 2$ consecutive schedule missing CT assessments	Date of last post-baseline CT assessment before missing CT assessment
Progression criteria met [REDACTED] after previous CT assessment	Date of previous CT assessment

OS is defined as the period from the first dose of study drug until death due to any cause.

Patients alive at their last visit will be censored at the last visit date.

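### SAP 7.8.6 and its Table 3 give different missing-scan rules for PFS, so some documented progressions are not events in the text and match no missing-scan row in the table

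*SAP*

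**What the plan says.** SAP 7.8.6 defines when progression counts as a PFS event. For RECIST, the first scan showing PD counts "if not more than one scheduled CT assessment is missing or not evaluable before this CT assessment" "and the previous CT assessment was performed within" a window that is redacted. For iRECIST, the same test is applied at the iUPD scan: "if not more than one scheduled CT assessment is missing or not evaluable before the CT assessment with iUPD documented". In neither sentence is the count limited to consecutive scans or to the interval just before the progression scan.

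The section then hands over to the table: "Patients without an event as defined above will be censored based on the rules in Table 3". Three rows of Table 3 matter here:

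- The general row: "No progression nor death nor non-trial systemic anti-cancer treatment documented", dated at the last post-baseline CT.
- The missing-scan row: progression criteria met after two or more "consecutive schedule missing CT assessments", dated "Date of last post-baseline CT assessment before missing CT assessment".
- A row for progression found too long after the previous CT, with the window redacted.

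None of them mentions not-evaluable scans.

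Scans are "planned for the visits at study weeks 9, 17, 25 (+/- 4 days), and from Week 25 onwards every 8 weeks" (SAP 7.8.1). Protocol 3.2.2 censors patients without progression or death at the last tumor assessment and has no missing-scan exclusion.

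**The concern.** The text decides whether there is an event, and the table dates everyone who has none. The two must therefore describe the same gap, and they do not. The text counts scans that are missing or not evaluable without asking whether they are adjacent. The table requires adjacency and counts only missing scans.

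The text count also grows with follow-up. The longer a patient stays on 8-weekly scans, the more likely two of them were missed or unreadable, and on the literal reading any progression after that no longer counts. The loss would fall on late progressions, which determine the 12-, 18- and 24-month estimates planned in SAP 7.8.7. The same progression date or PFS censoring rules feed time to response, duration of response and duration of disease control (SAP 7.8.4 and 7.8.5). Cohorts 2B and 3B have 7 and 5 patients, so one reclassified patient can visibly move a curve.

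**Working it through.** The SAP states no figure on this point, so there is none to reproduce. The check sets the two rules side by side and then sizes the difference under stated assumptions.

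**Worked cases**

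| Case | Text of 7.8.6 | Table 3 |
|---|---|---|
| (a) Weeks 9 and 25 missed, week 17 done, PD at week 33 | Two missing before PD: no event | Gaps not consecutive: missing-scan row not triggered. General row needs no documented progression: does not apply |
| (b) Weeks 17 and 25 scanned but not evaluable, PD at week 33 | Two not evaluable: no event | Scans were done: missing-scan row does not apply |
| (c) Weeks 17 and 25 missed, PD at week 33 | Criteria not met | Row plainly intended (date: week 9, day 57) begins by assuming the criteria are met |
| (d) Weeks 9 and 17 missed, PD at week 25 | Criteria not met | No post-baseline CT precedes the gap: the stated date does not exist |

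The redacted-window row might catch some of these; that cannot be checked.

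**When the rules can first differ (missing scans only).** Before PD at week 25 there are 2 earlier scheduled scans and 2² = 4 seen/missed patterns. None has two misses that are not adjacent. At week 33, 1 of 8 patterns does; at week 49, 7 of 32; at week 73, 46 of 256. So week 33 is the earliest split. Not-evaluable scans can split the rules sooner: two of them at weeks 9 and 17 already do so for PD at week 25.

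**Chance that a progression is voided.** Let q be the chance that a scan is missing or not evaluable. This is an assumption, independent across scans, at 10% (range 5 to 15%). With k earlier scans, the literal text voids with probability 1 − (1−q)^k − kq(1−q)^(k−1). A rule needing the two scans immediately before PD to be missing voids with probability q², from week 25 on.

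| PD at week | k | Text, q = 10% (5% to 15%) | Two immediately before, q = 10% |
|---|---|---|---|
| 25 | 2 | 1.0% (0.3 to 2.3) | 1.0% |
| 33 | 3 | 2.8% (0.7 to 6.1) | 1.0% |
| 49 | 5 | 8.2% (2.3 to 16.5) | 1.0% |
| 73 | 8 | 18.7% (5.7 to 34.3) | 1.0% |
| 105 | 12 | 34.1% (11.8 to 55.7) | 1.0% |

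Example, k = 3: 1 − 0.729 − 0.243 = 0.028.

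**Share of all detected progressions.** Assume exponential time to progression with median M and 13 scans at days t_j = 57, 113, …, 729 (t_0 = 0; 1 month = 30.4375 days). Progression falls between scans j−1 and j with probability 2^(−t_(j−1)/M) − 2^(−t_j/M). It is then detected at scan d ≥ j with probability q^(d−j)(1−q). Sum over j and d, and take the share with two or more misses before d (text) or with both scans d−1 and d−2 missed (consecutive). The medians come from Protocol 1.2 (2.1 and 2.6 months, two checkpoint-inhibitor trials in ACC), 1.1.3 (5.0, first-line chemotherapy in ACC) and 1.1.4 (8.9, sunitinib in MPP).

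| Median (months) | Text, q = 10% (5% to 15%) | Consecutive, q = 10% (5% to 15%) |
|---|---|---|
| 2.1 | 3.0% (0.8 to 6.1) | 1.7% (0.4 to 3.8) |
| 2.6 | 3.8% (1.1 to 7.6) | 1.9% (0.5 to 4.1) |
| 5.0 | 7.5% (2.3 to 14.1) | 2.2% (0.6 to 4.7) |
| 8.9 | 10.8% (3.4 to 19.6) | 2.3% (0.6 to 5.0) |

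Among progressions detected from the 7th scan (week 57) on, at q = 10%, the text voids 23 to 25% and the consecutive rule 3 to 6%. Those late detections are about 3 to 5% of the total at medians of 2.1 to 2.6 months and about 32% at 8.9 months.

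**The case against.** The best defence is that the text abbreviates the table. Its two conditions, a count of lost scans and a maximum distance to the previous CT, line up with the last two rows of Table 3. On that view both describe the gap just before the progression scan. The cumulative reading is literal but not the only one, and the documents do not settle which was meant. This stands, and it would dispose of case (a). It does not dispose of (b), (c) or (d).

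Second, the size is assumed. No miss rate is given, both windows are redacted, and SAP 5.3 is unreadable. At the ACC checkpoint-inhibitor medians the excess is only 1 to 2 percentage points. A later death within its redacted window, or the start of non-trial chemotherapy, can still be an event. These limits stand.

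Three stronger readings are tempting but unsupported:

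- A reader might infer that in case (c) the patient is censored at the PD scan, day 225, rather than at day 57, a difference of 168 days. The general row requires that no progression be documented, so Table 3 does not prescribe day 225.
- For the same reason, a reader might infer that Table 3 censors lost progressions at or after the PD scan. In case (a) it has no matching missing-scan or general row; the date would be improvised.
- A reader might infer that the phase 2 primary result is affected. SAP 4.4.1 gives that endpoint its own rule, with complete loss to follow-up counted as an event. For missing scans the two rules cannot differ before week 33.

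**Conclusion.** The conflict is real and should be resolved before programming. The text and Table 3 define the disqualifying gap differently, treat not-evaluable scans differently, and contradict each other on whether the progression criteria are met. The stated censoring date can also be undefined.

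If the text is programmed literally, documented late progressions are lost as events. Under the independent 10% miss rate and exponential model above, the loss is about 3 to 4% of detected progressions at medians of 2.1 to 2.6 months (about 2% under a consecutive rule), 7.5% at 5 months (2.2%) and 10.8% at 8.9 months (2.3%). It concentrates in long follow-up. The percentages illustrate the effect; they do not estimate this trial's loss. The affected outputs are secondary: PFS, duration of response, duration of disease control and time to response.

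**What to change.** Use one rule in both places. The gap rule should apply only when two or more consecutive scheduled assessments immediately before the PD or iUPD scan are missing or not evaluable. Specifically:

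- Delete the unqualified count from the two progression-criteria sentences, so that Table 3 alone handles lost scans.
- Add not-evaluable scans to the Table 3 missing-scan row.
- Date the censoring at the last evaluable assessment before the gap, or at first dose if there is none.

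A sensitivity analysis counting every documented progression, as Protocol 3.2.2 does, would be a useful addition.

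The cost is SAP wording and one programming condition; no new data are needed. Compared with literal programming of the text, some late PFS estimates become slightly less favourable.

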### **7.8.3 Best overall response, objective response, and disease control rate (DCR)**

OR is defined as the best overall response during the whole study period equal to PR or complete response (CR) according to RECIST [Eisenhauer et al] or as best overall response during the whole study period equal to immune partial response (iPR) or immune complete response (iCR) according to iRECIST. No confirmation of PR/CR and iPR/ iCR is required.

The ORR [%] is defined as the relative number of patients achieving OR according to iRECIST/RECIST in the respective cohort. The DCR [%] is defined as the relative number of patients achieving at least one assessment of iCR, iPR, or iSD according to iRECIST in the respective cohort or as the relative number of patients achieving at least one assessment of CR, PR, or SD according to RECIST.

The ORR/DCR according to iRECIST/RECIST will be summarized with two-sided 95% exact Clopper-Pearson CIs for binomial proportions by cohort.

The best overall response according to RECIST will be summarized by cohort, using the following categories and hierarchy: OR (RECIST) with subcategories CR and PR, SD, PD, not evaluable.

The best overall response according to iRECIST will be summarized by cohort using the following categories and hierarchy: OR (iRECIST) with subcategories iCR, iPR, iSD, iUPD, iCPD, not evaluable.

The disease control according to RECIST will be summarized by cohort, using the following categories and hierarchy: disease control (RECIST) with subcategories CR, PR, and SD, and PD, not evaluable.

The disease control according to iRECIST will be summarized by cohort using the following categories and hierarchy: disease control (iRECIST) with subcategories iCR, iPR, and iSD, and iUPD, iCPD, not evaluable.

The maximal shrinkage in tumor burden (i.e. maximal percentage decrease in sum of longest diameter compared to baseline = relative change from baseline) will be displayed

in a waterfall plot. The bars will be colored according to best overall response according to RECIST/iRECIST. Two different colors will be used for PD with new lesion and PD without new lesion. iUPD and iCPD will have the same color. Waterfall plots will be provided for Cohort 2A, Cohort 2B, Cohort 2, non-randomized, for Cohort 3A, Cohort 3B, Cohort 3, and Cohort 2A-I, Cohort 2A-II, and Cohort 2A-III, randomized, and for patients fulfilling and not fulfilling extended in/exclusion criteria (see Section 6.6) of Cohorts 2A, non-randomized.

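### SAP 7.8.6 does not fix a single iRECIST progression date when iUPD repeats before iCPD or is followed only by not-evaluable scans

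*SAP*

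**What the plan says.** SAP 7.8.6 gives two routes to an iRECIST progression date.

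- **Confirmed.** The date is that of an iUPD scan for which "the next CT assessment documents iCPD as response (without any intervening assessments with other outcome), i.e. PD is confirmed".
- **Unconfirmed fallback.** Where iCPD is lacking, the entry condition and its result read: "there is no subsequent CT assessment with iSD, iPR or iCR as response then the iUPD date will still be used". Two scenarios are listed. In the first, "no further response assessments are done or"; in the second, "the next timepoint responses are all iUPD, and iCPD never occurs".

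On unreadable scans, the iRECIST rule looks only backwards. It requires that "not more than one scheduled CT assessment is missing or not evaluable before the CT assessment with iUPD documented". It has no matching sentence for scans after the iUPD.

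Patients without an event go to Table 3. The row "No progression nor death nor non-trial systemic anti-cancer treatment documented" censors at the last post-baseline CT. The missed-scan row speaks of two or more "consecutive schedule missing CT assessments" and does not mention NE. SAP 7.8.3, by contrast, lists NE among the iRECIST response categories: "OR (iRECIST) with subcategories iCR, iPR, iSD, iUPD, iCPD, not evaluable".

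The protocol expects both scan histories. Table 9 in section 12.1 has a row iUPD, iUPD, iCPD, and a row iUPD followed by four NE scans whose best overall response is iUPD.

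**The concern.** There are two separate gaps.

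1. **Dating.** Followed word for word, the confirmed route picks the iUPD directly before iCPD. With two iUPDs before iCPD, that is the second one. The fallback dates the same two iUPDs, if never confirmed, at the first. Stronger evidence of progression would then give a later progression date.
2. **NE after iUPD.** An iUPD followed only by NE scans passes the fallback's entry condition, because no iSD, iPR or iCR follows. If NE counts as an assessment, however, neither listed scenario fits: assessments were done, and they were not all iUPD. The patient can then be censored under Table 3. The same iUPD with no later scan at all is an event, so an unreadable scan, which says nothing against progression, would remove an event.

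The date feeds secondary iRECIST PFS and its Kaplan-Meier (KM) estimates (SAP 7.8.7), duration of response and of disease control (7.8.5), and the censoring date for time to response (7.8.4). Two programmers could derive different values from the same data.

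**Working it through.** The documents state no figure to reproduce, so the check applies the rule to scan sequences.

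**Inputs**
- CT at weeks 9, 17, 25 and every 8 weeks after (SAP 7.8.1). Day = 7 × (week − 1) + 1, giving days 57, 113, 169, 225 and 281. Week 25 as day 169 agrees with SAP 4.4.1.
- 6 months = 6 × 30.5 = 183 days. The 30.5-day month is in SAP 7.3 and 7.4.1; using it for the KM time point is an assumption.
- Cohort 2A-I has 13 patients (SAP 4.2).
- The blacked-out time limits in 7.8.6 and Table 3 were not applied.

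**Dates, first iUPD at week 9**

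| Scan sequence | One reading | Other reading |
|---|---|---|
| iUPD, nothing after | event day 57 | same |
| iUPD-iUPD, never confirmed | event day 57 | same |
| iUPD-iUPD-iCPD | literal: event day 113 | first iUPD of the run: event day 57 |
| iUPD-NE | NE an assessment: no event, censored day 113 | NE not done: event day 57 |
| iUPD-NE-NE-NE-NE | NE an assessment: no event, censored day 281 | NE not done: event day 57 |

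The dating gap is 113 − 57 = 56 days, and each further iUPD before iCPD adds 56 days on the literal reading.

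**Size of the NE gap, illustration only.** Assume 13 patients, six other events by day 183, nobody else censored earlier, and one patient with iUPD at day 57, NE at day 113 and nothing later.
- Counted as an event: 6/13 = 46.2%, whenever the other six events fall.
- Censored at day 113, other events all at day 57: 7/13 = 53.8%.
- Censored at day 113, two other events each at days 57, 113 and 169: (11/13) × (9/11) × (6/8) = 51.9%.
- Censored at day 113, other events all at day 169: 6/12 = 50.0%.

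If three other patients are instead censored at day 1 and the six other events are all at day 57, ten patients are at risk. The estimates are then 3/10 = 30% and 4/10 = 40%, a larger gap.

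**When the dating gap moves the 6-month estimate**
- *The two dates fall on either side of day 183.* With iUPD at weeks 25 and 33 then iCPD, they are day 169 and day 225. With iUPD at weeks 17, 25 and 33 then iCPD, they are day 113 and day 225.
- *Another patient is censored between the two dates.* With 13 patients, one of them censored at day 85 (assumed) and no other event, an event at day 57 gives 12/13 = 92.3% and at day 113 gives 11/12 = 91.7%. Other patients' events in between change the curve there, but without such censoring they leave the 6-month value unchanged.

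**The case against.** On dating, the defence is good. If the very next CT must be iCPD, nothing can intervene, so the parenthesis about intervening assessments is redundant unless the rule looks back over an unbroken run of iUPDs. SAP 7.8.6 ends PFS at the earliest qualifying event, and 7.8.5 ends iRECIST response duration at the earliest date the criteria are met. Both favour the first iUPD. A reader might infer that the SAP definitely postpones confirmed progression; the text does not support that. What stands is that the first-iUPD rule is never stated and the literal words give another date. The instruction in protocol section 12.1 to use the earlier date once progression is confirmed is weak support either way, because it concerns equivocal progression under RECIST 1.1.

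On NE, one can argue that an unreadable scan yields no response assessment, that 7.8.6 already groups missing with NE before the iUPD, and that a Table 3 row for patients without documented progression fits badly when an iUPD is on record. That reading is reasonable. But 7.8.3 and protocol Table 9 treat NE as a recorded response, and the missed-scan row omits it, so the SAP points both ways.

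It is also fair that an eligible death or the start of chemotherapy can still give a PFS event, that all response assessments are listed so affected patients can be found, and that no direct statistical comparison between the randomized groups is planned. These points limit the consequence; they do not supply the missing rule.

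**Conclusion.** The point holds as a minor drafting gap. Part 1 is an ambiguity whose literal reading gives the wrong date, 56 days late per extra iUPD. Part 2 is a missing rule: the same iUPD is an event or a censored observation depending on how NE is read. The visible redactions sit where time limits belong and do not appear to hide an NE rule.

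Three stronger inferences are tempting but unsupported:
- *That the phase 2 primary result is affected.* The visible text of SAP 7.8.2 counts patients alive with iUPD or iCPD as having progressive disease, and the rest is redacted. No effect is claimed there or on RECIST 1.1 PFS.
- *That one patient in 13 caps the shift at 1/13 = 7.7 points, or that dating matters only when the first iUPD is at week 25.* The 30% against 40% example and the weeks 17-25-33 example show otherwise.
- *That many patients are involved.* Table 9 shows that these sequences are foreseen, not how often they occur; the documents give no count. An iUPD-NE-iCPD sequence has the same gap, but the 4-to-8-week confirmation window and the Table 8 footnote, which ties a prior iUPD to the assessment immediately before, should make it rare.

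The 46.2% against 50.0% to 53.8% figures rest wholly on the assumed event pattern.

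**What to change.** Add to SAP 7.8.6, in substance: *The iRECIST progression date is the first iUPD of a run not reset by a later iSD, iPR or iCR, whether the run ends in iCPD, in further iUPD only, or with no further evaluable assessment. NE scans after that iUPD are treated as not done. The missed-CT and maximum-gap conditions apply to the interval before that first iUPD.*

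In Table 3, exclude an iUPD that was never reset from the no-progression row, and say in the missed-scan row whether NE counts as missing. Footnote the number of events that rest on an iUPD followed only by NE.

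The cost is a few sentences, two table edits, one footnote and a small change to the derivation program, with no new data. The downside is that iRECIST PFS may come out slightly shorter, and a few unconfirmed iUPDs that could be pseudoprogression will count as events; the footnote discloses these. Counting them is a convention. If the sponsor prefers another, stating it explicitly would also close the gap.

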## 3.2 Study endpoints

### 3.2.1 Primary endpoint

- ***The primary endpoint of the phase 1 part*** includes safety and tolerability of EO2401 in combination with nivolumab by a descriptive medical assessment of the combined profile of incidences of adverse events (AEs), treatment-emergent AEs (TEAEs), serious AEs (SAEs), deaths, reasons for treatment discontinuation/delays, and laboratory abnormalities using the NCI-CTCAE v5.0 grading system [60].
- ***The primary endpoint of the phase 2 part*** is the rate of patients without progression (according to iRECIST criteria [37]) or death due to any cause at 6 months after the first dose of randomized treatment. Six months after the first dose of randomized treatment will be determined for each patient and is dependent on the exact time point of evaluation of the CT investigation scheduled at week 25 (day 169). The primary endpoint is to be determined per investigator/local site assessments of progression. The denominator will be all patients who started the randomized treatment in Cohort 2A\* and will be determined for each randomized treatment group separately. Patients will be followed up for progression or death during the first 6 months after start of randomized treatment regardless of whether they stop treatment and continue on other regimens. Patients who

are completely lost to follow-up will be counted as if they had a PFS event during the first 6 months.

\* Cohort 2A = patients with ACC who had prior systemic therapy for established locally advanced or metastatic disease

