Of special note, unlike RECIST 1.1, the iRECIST criteria requires the confirmation of progression and uses the terms iUPD (unconfirmed progression) and iCPD (confirmed progression). Confirmatory scans should be performed at least 4 weeks, but no longer than 8 weeks after iUPD. Thus, in the current trial, provided that the individual patient is tolerating the administered treatment adequately, it is allowed continuing trial treatment beyond progression as assessed by the RECIST 1.1. criteria for evaluation of progression according to the iRECIST criteria. Provided good tolerability of the trial treatment and lack of new important symptoms indicating clinical tumor progression the confirmatory scans might be obtained at the current trials planned 8 weekly tumor assessment timepoints.

In the context of confirmation of PD per iRECIST, and the timeline of confirmatory scans to be performed at least 4 weeks, but no longer than 8 weeks after iUPD, it should be specifically noted that in case of any signs of rapidly progressing disease establishment of PD and a following therapy switch should be made also earlier than 4-8 weeks after iUPD when necessary.

For all cohorts, and all patients during the whole trial treatment, the following safety rules will apply:

[figure not shown]

Details of the IDMC process and procedures, and Cohort management plan are outlined in a separate Charters.

The schematic trial and cohort designs are presented in [Figure 6](#) and [Figure 7](#).

[figure not shown]
Protocol No: EOADR1-19  
EudraCT: 2019-003396-19

CONFIDENTIAL

Protocol No: EOADR1-19  
EudraCT: 2019-003396-19

CONFIDENTIAL

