#### **7.8.5 Duration of response (DOR) & Duration of disease control (DDC)**

DOR can only be determined for patients with OR as defined above.

According to RECIST, the DOR is measured from the time at which the measurement criteria according to RECIST are first met for CR or PR (whichever is first recorded) until the first date that PD is objectively documented according to RECIST (see Section 7.8.6 for details).

- According to iRECIST, the DOR is measured from the time at which the measurement criteria according to iRECIST are first met for iCR or iPR (whichever is first recorded) until the first date progression criteria according to iRECIST are met (see Section 7.8.6 for details).

Patients alive with no progression will be censored following the same censoring rules as for PFS (see Section 7.8.6). DDC can only be determined in patients with disease control as defined above. DDC according to RECIST/iRECIST is measured from the start of study treatment until the first date that PD is objectively documented according to RECIST/iRECIST (see Section 7.8.6 for details); alternatively censoring is applied according to the rules for PFS.

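### SAP 7.8.6 lets a CT taken after the start of other anti-cancer therapy cancel an earlier unconfirmed iUPD, so an iRECIST progression can be lost or post-dated

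*SAP*

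**What the plan says.** **Progression rule.** SAP 7.8.6 dates iRECIST progression at an iUPD when the next CT is iCPD. For an unconfirmed iUPD it adds: "If progression is not confirmed and there is no subsequent CT assessment with iSD, iPR or iCR as response then the iUPD date" is still used, in two scenarios: no further assessment is made, or all later assessments are iUPD. Nothing is said about the treatment the patient is receiving at the later CT.

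**Scans admitted.** SAP 7.8.1 uses local assessments "regardless of whether they come from scheduled or unscheduled assessments and if they were assessed during or after study treatment", and CTs continue every 8 weeks in patients who stop all study treatment without confirmed PD. The data review meeting decides whether scans after further anti-cancer treatment are used, but that clause concerns treatment given before the patient's study treatment ended.

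**Switching before confirmation.** For the interval between an iUPD and its confirmatory scan, Protocol 4.2 provides, where needed: "in case of any signs of rapidly progressing disease establishment of PD and a following therapy switch should be made also earlier than 4-8 weeks". Protocol 7.7 and Appendix 1 repeat this. For the 6-month endpoint, Protocol 3.2.1 follows patients "regardless of whether they stop treatment and continue on other regimens".

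**New therapy as an event.** SAP 7.8.6 also lists as a PFS event: "Start of non-trial systemic anti-cancer treatment (which is regarded as progression according to the protocol". This is limited to treatment "that is classified as chemotherapy in the eCRF", and "Mitotane therapy is not considered as non-trial system anti-cancer treatment".

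**Durations.** Under SAP 7.8.5, iRECIST duration of response runs "until the first date progression criteria according to iRECIST are met", with reference to 7.8.6.

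**The concern.** Confirmation of progression is in iRECIST to separate pseudoprogression under immunotherapy from true progression (Protocol 4.4 and Appendix 1). A scan can serve that purpose only while its result can be attributed to the trial treatment. Once the patient is on another therapy, regression may be due to that therapy, yet the SAP lets the scan remove the earlier iUPD.

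The mechanism works in one direction: it can delay or delete an iRECIST event but cannot create one. It also applies where the protocol foresees a switch before confirmation, which is in patients with signs of rapid progression. At stake are the iRECIST versions of PFS, duration of response (DOR) and duration of disease control (DDC), and possibly the 6-month PFS rate.

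**Working it through.** The plan states no figure on this point, so the check applies the rules to test histories.

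**1. What it takes to cancel an iUPD.** Protocol Appendix 1 keeps a patient at iUPD if the progression criteria are still met without worsening. It assigns iSD, iPR or iCR only if those criteria are met against baseline. Table 8 likewise leaves unchanged progression, and unchanged new lesions, at iUPD. Illustration with baseline as nadir:
- Baseline sum 100 mm; progression threshold = 100 × 1.20 = 120 mm (and an increase of at least 5 mm).
- iUPD at 130 mm.
- Next scan on new therapy still 130 mm: iUPD again. If all later scans are also iUPD, SAP 7.8.6 keeps the first iUPD date.
- Next scan below 120 mm, with no non-target progression and no new lesion: iSD. The iUPD is cancelled.

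So the patient must regress below the threshold.

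**2. Test patient.** Scans follow the SAP 7.8.1 schedule: week 9 = day 57, week 17 = day 113, week 25 = day 169. Suppose iUPD on day 57, study treatment stopped, other therapy started on day 75, and iSD through regression on days 113 and 169.

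| History | iRECIST PFS under the SAP as written | If post-switch scans cannot reset |
|---|---|---|
| New therapy coded as chemotherapy | Event day 75 | Event day 57 |
| Other systemic agent not so coded, mitotane, or local therapy | No event; censored day 169 | Event day 57 |
| iUPD, no further scan | Event day 57 | Event day 57 |
| iUPD, then iCPD on day 113 | Event day 57 | Event day 57 |

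In the first row the event is post-dated by 75 − 57 = 18 days. In the second it is lost, or replaced by a later event if the patient progresses again.

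**3. DOR and DDC.** Both end at progression as described in 7.8.6. Starting new therapy is listed there as a PFS event, separate from the iRECIST progression criteria. A responder with a later iUPD that is cancelled after a switch may therefore have a duration running past that iUPD. The text does not make clear whether even coded chemotherapy ends it.

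**4. The 6-month rate.** Cohort 2A-I has 13 treated patients (SAP 4.2). One patient is 1/13 = 7.7 percentage points. Exact Clopper-Pearson 95% limits are the 0.025 quantile of Beta(x, 13 − x + 1) and the 0.975 quantile of Beta(x + 1, 13 − x):

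| Progression-free | Rate | 95% CI |
|---|---|---|
| 2/13 | 15.4% | 1.9 to 45.4 |
| 3/13 | 23.1% | 5.0 to 53.8 |
| 4/13 | 30.8% | 9.1 to 61.4 |

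These counts are illustrations, not trial results.

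**The case against.** **Most switches are already handled.** In part. Coded chemotherapy is itself a PFS event, so that patient is not counted as event-free; only the date is wrong. The data review meeting also confirms which treatments count as non-trial systemic therapy. But the definition is confined to chemotherapy as coded in the eCRF, mitotane is exempt, and local therapy falls outside it.

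**Stabilising on rescue does not cancel an iUPD.** This stands. A reader might infer that anyone who progresses, switches and then stabilises is recorded as never having progressed. Appendix 1 and Table 8 do not support that, as step 1 shows.

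**The 6-month endpoint may be untouched.** This also stands as a limit. The readable part of SAP 7.8.2 puts patients alive with iUPD or iCPD among the failures, does not list new therapy, and does not visibly import the 7.8.6 rule. The assignment rule is largely redacted, so a bias in that rate cannot be asserted.

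**The protocol chose to follow patients through other regimens.** True, but continuing to look for events after a switch does not imply that an event recorded before the switch should be undone. Protocol 6.9.3 points the other way: new systemic therapy leads to censoring at its start, or to PD if the criteria are met.

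**Little depends on it.** SAP 7.8.2 treats the first Simon stage as already read out without success and plans only counts and an exact interval, so no continuation decision remains. RECIST 1.1 PFS has no cancellation rule and is unaffected. This lowers the priority; the iRECIST estimates will still be reported.

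**Conclusion.** The gap is real but narrow, and should be fixed. As written, SAP 7.8.6 can erase or post-date an iRECIST progression when the patient regresses below the progression threshold on another anti-cancer therapy. The PFS event is lost or replaced by a later one after rescue not coded as chemotherapy, and moved to the therapy start after coded chemotherapy. iRECIST DOR and DDC may be extended.

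The 6-month rate is affected only on the assumption that 7.8.2 uses the same derivation; each affected patient is then worth 7.7 points. The total effect cannot be estimated: the documents do not give the number of patients who switch after iUPD, and the effect is zero if none fits the pattern.

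A reader might try to size the effect by multiplying an assumed number of switchers by the first-line EDP-M response rate in Protocol 1.1.3, or by a disease control rate. The documents do not support this. The number of switchers would have no source. EDP-M is chemotherapy, so if coded as such its start is already a PFS event. Disease control measured from the post-progression level would mostly still be scored iUPD.

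**What to change.** Add to SAP 7.8.6, and apply to DOR and DDC and, if the same derivation is used there, to the 6-month rate:

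> *CT assessments after the start of any other anti-cancer treatment (systemic or local) cannot reset an earlier iUPD. If the iUPD was not followed by iSD, iPR or iCR before that start, the iUPD date is the iRECIST progression date.*

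State also whether mitotane that is started or restarted after the iUPD counts as other treatment; SAP 7.6 already separates continued from restarted mitotane. Flag affected patients in the response listing.

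Reconcile the new-therapy event in 7.8.6, which the SAP attributes to the protocol, with Protocol 6.9.3, which prescribes censoring, or PD if the criteria are met.

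The cost is SAP wording and programming. Scans and further anti-cancer treatments are already collected (Protocol 7.5.2 and 7.5.3). The downside is that a true pseudoprogressor who switched early counts as progressed, so iRECIST PFS may look slightly less favourable.
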